The present study will be conducted in multiple independent outlets in the UK OOH food sector and examine the impact of NS menu labelling. Participants will visit an outlet and be randomized to order from the restaurant's menu with calorie information or a menu with calorie information and NS labelling. The main objective of this study is to assess differences in PME according to labelling condition. Secondary objectives are to measure the effect of NS labels on the nutritional quality of food selected (UK NPM scores), energy content of the meal (both ordered and consumed) and likelihood of selecting a healthier and a less healthy option. Whether impacts of NS labelling differ based on participant characteristics will be explored (Socioeconomic Position (SEP), food choice motives) and we will also examine later food intake to assess whether there is any evidence of between condition differences (e.g., compensating for healthier meal choice in the NS condition by consuming less healthy food later in the day).

Study Information

Hypotheses:

Participants in the NS with calorie labelling condition will score higher on PME relating to the menu compared to participants in the calorie labelling only condition.

Participants in the NS with calorie labelling condition will order a meal with greater nutritional quality compared to participants in the calorie labelling only condition.

Participants in the NS with calorie labelling condition will order fewer calories from food overall compared to participants in the calorie labelling only condition.

Participants in the NS with calorie labelling condition will be more likely to choose healthier items (categorised as A/B) from the menu, and less likely to choose less healthy items (categorised as D/E) from the menu compared to participants in the calorie labelling only condition.

Design Plan

Study type: Experiment - A researcher randomly assigns treatments to study subjects; this includes field or lab experiments. This is also known as an intervention experiment and includes randomised controlled trials.

Blinding: Participants will not know the treatment group to which they have been assigned.

Is there any additional blinding in this study? To attempt to reduce the likelihood of aim guessing, participants will be recruited to a study described as 'A study of consumer behaviour in different restaurants'.

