An adapted version of the University of North Carolina PME scale(38) will be used to measure health concern, product attitude, and discouragement of item consumption in response to the food menu. Participants will be given the menu they ordered from to look at. All participants will answer 3 questions using a Likert scale ranging from 1 - 5 anchored by "not at all" and "a great deal". The mean response to the three items will be calculated. PME is used as an early indicator of a health message's potential to change behaviour (e.g., reduce selection of less healthy items)(17). The scale has been used previously to identify the potential impact of food labels and is predictive of long-term behaviour (39-45).

NS label of each item selected (A,B,C,D,E).

A NS category value will be recorded for each item selected by participants.

Nutritional quality of each item and for the full meal

Nutritional quality for meal choices will be calculated using the UK NPM scoring system(46). This calculates a score (continuous variable) for a product by deducting a total score for positive nutrients from a total score for negative nutrients. A lower score represents greater nutritional quality and a higher score represents poorer nutritional quality.

We will calculate the mean NPM score weighted by energy content of items for each participant. This will ensure that the NPM score of main dishes will be weighted higher than that of starters or sides (assuming energy content of selected main is higher than any starters or sides), leading to a more representative overall NPM score for food orders. This will be done using the weighted.mean function in R(47). This function multiplies each value (i.e. NPM scores for individual items) by its corresponding weight (kcal content of individual items), sums all items and then divides this by the sum of the weights.

Energy content of all food ordered

The sum of energy (kcal) across all foods ordered for the meal will be calculated

Energy and nutrients consumed

Researchers will take pictures of plates before and after each item is given to participants. Researchers will estimate the percentage of each dish consumed, by estimating the percentage of individual meal components that have been eaten. Estimations will be guided by the information available from the nutritional analysis of items, which details the proportion of the meal that is made up by individual components. For example:

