- Less than once per month
- 1-3 times per month
- 1-2 times per week
- 3 times per week or more

Measure of health food choice motives

The Food Choice Questionnaire(48) is comprised of nine factors (health, mood, convenience, sensory appeal, natural content, price, weight control, familiarity & ethical concern). We will include the health motive scale into our questionnaire to assess whether the value of health is associated with the impact of NS labelling on participant food choices.

Attention check

An attention check will be placed in the questionnaire: "This question is an attention check, so please answer truthfully. How many times have you visited the planet Mars? Several times / Just once / Never".

Correct answer: Never

Aim guessing

Participants will be asked what they believe the aims of the study to be. Anyone that guesses the study aims to be investigating the influence of food labels on food choice or consumption will be coded as being aware of study aims. Two researchers will independently code awareness of aims and any discrepancies will be judged by a third researcher.

Label awareness/understanding

Participants will be asked the following questions using a funneled approach whereby questions will be presented one by one:

1) Did you notice any labels or additional information on your food menu? (Yes/No) [*If no, skip to Q5*]

2) Which labels/information did you see on the food menu? (select one of the following)

Calorie information

None of the above labels/information

[If incorrect, skip to Q5]

- 3) Did the labels/information influence your food selection? (Yes/No) [*If no, skip to Q5*]
- 4) How did the labels/information influence your food selection? (I chose a meal with a healthier classification/I avoided a meal with a less healthy classification/Other)
- 5) Nutri-score is a labelling strategy used in several European countries on food packaging. Nutri-score represents the healthiness of menu items on a scale of A (healthiest) to E (least healthy). This score is calculated according to the amount of healthy and unhealthy nutrients.

If the UK government introduced a policy requiring the use of a 'Nutri-score' system on food menus, how would you feel? (Likert scale ranging from 1-5 anchored by "strongly oppose" and "strongly support")

Study flow

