	Control condition Participants will receive a calorie labelled menu without NS labels. The menu will include a statement that 'Adults need on average 2000 kcal per day'.	Experimental condition Participants will receive a menu with each item labelled with calorie content and a NS value (A to E, where A is the healthiest in dark green and E is the least healthy, in red). The menu will include a statement that 'Adults need on average 2000 kcal per day'. Text at the bottom of the menu will show the full Nutri-score diagram and read: " NUTRI-SCORE NUTRI-SCORE NUTRI-SCORE NUTRI-SCORE NUTRI-SCORE NUTRI-SCORE NUTRI-SCORE NUTRI-SCORE NUTRI-SCORE NUTRI-SCORE NUTRI-SCORE NUTRI-SCORE This score is calculated according to the content of energy and key dietary nutrients (e.g. saturated fat, sugar, salt, protein, fibre). This does not differentiate between fructose (i.e. sugar found in fruit) and refined sugar or directly account for vitamin/mineral contents or level of processing"			
	 The participants will be asked to order lunch from the menu. The procedure of placing orders will be finalised with the restaurant staff. When meals are ready, researchers will take a picture of each plate of food and serve to participants. A second photo of each plate will be taken when meals are finished, and plates are cleared. 				
Post-meal assessments (Qualtrics)	After finishin iPad to comp will ask them	g their meal, participants will be provided with an olete a follow-up questionnaire (Appendix D), which it o guess the aim of the study, collect information on essage effectiveness, health food choice motives,			

	demographic characteristics, and label awareness and understanding.
Reimbursement	 Participants will pay for their meals individually before being asked to complete a payment form. Participants will receive reimbursement for their time and travel and serve as an incentive for people from different SEP strata to participate.
Later intake	• After the restaurant visit (the next morning), participants will receive a link to Intake 24, an online programme used for dietary recall. This will be used to estimate intake for the remainder of the day after the study session.
Debrief	• Participants will be sent a debrief sheet which will detail the full aims of the study. (Appendix E)

Analysis Plan

Participant characteristics:

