 - □ White English/Welsh/Scottish/Northern Irish/British
 - White Irish
 - □ Any other White background
 - □ White and Black Caribbean
 - □ White and Black African
 - □ Any other mixed/multiple ethnic background please describe
 - Indian
 - Pakistani
 - Bangladeshi
 - □ Chinese
 - Other Asian
 - African
 - □ Caribbean
 - 🗆 Arab
 - □ Any other ethnic group
- 14. What is your weight
 - 🗆 In KG _____
 - In Stone and pounds _____
 - Prefer not to say

15. What is your height

- In centimetres_____
- In feet and inches _____
- Prefer not to say

[figure not shown]
16. How often, on average, over the past year have you eaten out (e.g., at a restaurant, café)?

- □ Not in the last year
- □ Less than once per month
- □ 1-3 times per month
- □ 1-2 times per week
- □ 3 times per week or more

17. Did you notice a label on the food menu? [If no, skip to Q21]

- 🗆 Yes
- 🗆 No

18. Which labels/information did you see on the food menu? (select one of the following) [If incorrect, skip to Q21]

19. Did the label/information influence your food selection? (Yes/No) [If no, skip to Q21]

Yes

🗆 No

[figure not shown]
20. How did the label/information influence your food selection?

- a. I chose a meal with a healthier classification
- b. I avoided a meal with a less healthy classification
- c. Other

21. Nutri-score is a labelling strategy used in several European countries on food packaging. Nutri-score represents the healthiness of menu items on a scale of A (healthiest) to E (least healthy). This score is calculated according to the amount of healthy and unhealthy nutrients.

If the UK government introduced a policy requiring the use of a 'Nutri-score' system on food menus, how would you feel? (Likert scale ranging from 1-5 anchored by "strongly oppose" and "strongly support")

22. [PME measure - participants in both conditions (calorie labels/NS with calorie labels) will be given the menu they ordered from].

Please look at the menu you were given, and think about the menu.

"The menu made me concerned about the health effects of consuming less healthy menu items"

- □ Strongly disagree
- □ Slightly disagree
- □ Neither agree nor disagree
- □ Slightly agree
- □ Strongly agree

"The menu made consuming less healthy items seem unpleasant"

- □ Strongly disagree
- Slightly disagree
- □ Neither agree nor disagree
- □ Slightly agree
- □ Strongly agree

"The menu discouraged me from wanting to consume less healthy items".

- □ Strongly disagree
- □ Slightly disagree

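### PME, the main-objective outcome, is given two different response scales, and Appendix D has it rated straight after a Nutri-Score description shown to both arms

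*Protocol*

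**What the plan says.** The introduction to the protocol states: "The main objective of this study is to assess differences in PME according to labelling condition". The Sample size section treats PME as one of two primary outcomes.

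**Response format.** Measured variables (Perceived Message Effectiveness) has all participants answer three items on a "Likert scale ranging from 1 - 5 anchored by 'not at all' and 'a great deal", and the three answers are averaged. Appendix D, Q22 prints five options under each item, from strong disagreement to strong agreement, with "Neither agree nor disagree" in the middle.

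**Order.** PME is the last question in Appendix D: "22. [PME measure - participants in both conditions (calorie labels/NS with calorie labels) will be given the menu they ordered from". The question before it begins "21. Nutri-score is a labelling strategy used in several European countries on food packaging", explains that A is healthiest and E least healthy, and asks about support for a government Nutri-Score policy on menus. The skip rule at Q17 reads "17. Did you notice a label on the food menu? [If no, skip to Q21", and Q18 and Q19 also skip to Q21. The Label awareness/understanding section describes the same funnel ("Participants will be asked the following questions using a funneled approach whereby questions will be presented one by one"), with the policy item as its fifth question and the target of every skip.

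**What each arm has already seen.** Under Study flow, the control arm is described as follows: "Participants will receive a calorie labelled menu without NS labels". The Nutri-Score menu shows the full diagram and a text on how the score is calculated.

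**The concern.** The two formats ask for different judgements. One runs from none to a lot; the other runs from disagreement through neutral to agreement. Only one can be fielded, and the protocol fixes the instrument twice, differently. The power statement for PME rests on a mean, an SD and an effect that belong to whichever format produced them. If the questionnaire uses the other format, those values may not carry over.

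The order is a separate matter. PME is self-reported and is meant to capture the response to the menu. Just before rating it, controls are told about a labelling system their menu lacked and are asked for an opinion on it. The Nutri-Score arm has already had that explanation on its menu. A difference between arms could then arise partly from the questionnaire. It could not be separated from the label effect afterwards. The planned analysis with and without participants who guessed the aim does not help, because the aim guess is Q4 and comes long before Q21.

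**Working it through.** **1. Do the two descriptions of the scale agree?**

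| Feature | Measured variables | Appendix D, Q22 |
|---|---|---|
| Items | 3, averaged | 3 |
| Points | 5, numbered 1 to 5 | 5, no numbers printed |
| Low end | not at all | strongly disagree |
| Middle | no label given | neutral |
| High end | a great deal | strongly agree |

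The number of items and points agrees; the anchors do not.

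**2. What do the planning values mean on each scale?** Sample size gives a control mean of 1.85 and an effect of 1, so the planned Nutri-Score mean is 1.85 + 1 = 2.85. Scored 1 to 5 on the Appendix D options, both means lie below the neutral point of 3, on the disagree side. On the amount anchors, 2.85 is simply a rating above the lowest point. This does not reveal which format was the source; it shows that the same numbers describe different responses.

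**3. Who reads Q21 before Q22?** The skips at Q17, Q18 and Q19 lead to Q21, and Q20 runs on to it. Q21 carries no condition by arm. Every respondent therefore reads it directly before PME.

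**4. Reproducing the stated power.** Inputs from Sample size: 20 days of 20 participants, SD 1.08, ICC 0.200, effect 1. Two-sided 0.05 is assumed, as sidedness is not stated. Reading 1.08 as the residual SD and the ICC as by day:

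- Day variance = (0.2/0.8) × 1.08² = 0.2916, so the day SD is 0.54.
- SE = √[(0.2916 + 1.1664/20) × 2/10] = 0.2645.
- Power by noncentral t on 18 df = 94.6%, against the stated 94%.
- The exact 95% interval for 188 of 200 simulations is 89.75% to 96.86%, as stated.

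This is one reading of the inputs; it leaves out the eating-group SD of 1.

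**5. Sensitivity to the true difference.** The differences below are assumptions; the protocol gives no figure linking the anchors or the order to a loss of effect. The SE implied by 94% power at a difference of 1 is 1/(1.960 + 1.555) = 0.2845. Power at difference d is P(Z > 1.960 − d/SE). The middle column starts from the lower simulation limit of 89.75% (SE 0.310).

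| d | SE 0.2845 | SE 0.310 | Rebuilt design, t on 18 df |
|---|---|---|---|
| 1.0 | 94.0% | 89.75% | 94.6% |
| 0.9 | 88.6% | 82.8% | 89.5% |
| 0.8 | 80.3% | 73.3% | 81.6% |
| 0.5 | 42.0% | 36.5% | 43.2% |

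A larger difference would help: d = 1.1 gives 97.2% with SE 0.2845. The anchors could also change the spread. In the rebuilt design with d = 1, an SD of 1.2 gives about 90% and an SD of 1.4 about 79%.

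**The case against.** Whichever scale is fielded goes to both arms, so the mismatch alone does not bias the randomised comparison, and a five-point mean can be computed from either. That stands: this part concerns defining the outcome and matching the planning values to it.

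The loss of power is not demonstrated. The values are said to rest on previous research, and the protocol does not show which anchors that research used. The sensitivity table describes the simulated 400 participants at 0.05, whereas the plan raises the target to 450 and adjusts p values if recruitment continues past the interim analysis. This also stands, and the table is illustrative only.

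On order, Q22 asks about the menu the participant was given, with that menu back in hand, which ties the rating to the assigned menu. No size or direction of effect can be shown. The Procedure and Study flow sections also list PME ahead of some other topics. Neither says that its list is the order of presentation, however, and Appendix D is the only instrument shown. The re-shown menu lessens the worry without removing the unequal exposure just before the rating.

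Finally, moving PME ahead of Q21 still leaves it after Q17 to Q20, which already direct attention to labels. That is true, and the remedy is partial.

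**Conclusion.** The concern holds. The protocol contradicts itself on the response scale of its main-objective outcome. Its only questionnaire also places a Nutri-Score description, new mainly to controls, immediately before that outcome is rated. Both facts are plain in the text; their effect on the result is not known.

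No bias can be quantified, and the 94% power is not shown to be wrong. It is conditional on the fielded scale behaving like the source scale. If the true difference were 0.8 instead of 1, power would be about 80% with the implied standard error held fixed; at 0.5 it would be about 42%. Both differences are assumed. This should be fixed before data collection because it touches a primary outcome and costs almost nothing.

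**What to change.** 1. Swap Q21 and Q22 in Appendix D, so that PME becomes Q21 and the Nutri-Score policy item becomes Q22. The existing skips to Q21 then land on PME, and the noticing items Q17 to Q20 still come before the menu is shown again. In Label awareness/understanding, state that the fifth item is asked after PME.
2. Choose one set of anchors, preferably that of the study behind the planning values, and state it identically, with its 1 to 5 coding, in Measured variables and Appendix D.
3. In Sample size, confirm that 1.85, 1.08 and the effect of 1 come from that format. If they do not, restate the PME power over a range of effects and SDs.

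The cost is one swap and one relabelling in the online questionnaire, matching text edits and a check of the planning source. No extra participants or staff are needed. The small downside is that policy support would be asked after PME, with the menu just re-read.

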Appendix E: Debriefing text

In this study we were interested in the effect Nutri-score labels on perceived effectiveness of labels, food choice and consumption. Nutri-score labels are used on food packaging in a number of European countries.

In order to categorise items, scores are calculated by considering the healthy aspects of an item (e.g. fibre, protein, fruit, vegetable and nut content) and the less healthy aspects (e.g. salt, sugar, fat and saturated fat). Scores correspond to a letter where A (dark green) represents the healthiest items and E (red) represents the least healthy items.

Participants were presented with a regular menu, or a menu where all items were given a Nutriscore categorisation.

We wanted to investigate whether being shown a menu with Nutri-score would make people rate the menu as more effective in terms of communicating the healthiness of items. We also wanted to see if being shown the menu made participants more likely to select a healthier option and order fewer calories.

Finally, we wanted to see if being provided with Nutri-score labels was associated with later intake. Specifically, if healthier choices are made at lunch time, are these compensated for later in the day (e.g. by eating unhealthy food or more food later on).

The questionnaire about food choice motives and compensatory health beliefs will be used to test any characteristics and motivations that may impact the amount of food eaten.

If this study has raised any issues regarding your weight or eating behaviours, we recommend contacting your doctor.

The following NHS page provides information and guidance on eating a healthy, balanced diet: https://www.nhs.uk/live-well/eat-well/

Thank you very much for your participation in our study.

References

1. Beth Armstrong LK, Robin Clifford, Mark Jitlal, Katie Mears, Charlotte Parnell & Daniel Mensah. F&Y2 Wave 6. UK: Food Standards Agency; 2023.

